2 INTRODUCTION AND RATIONALE

Since 1996, approximately 18 million Americans have undergone LASIK (see Figure 1).¹ With the average age of LASIK patients having remained stable at between 35 and 40 years of age, this means that the post-LASIK population is increasingly entering the age range for cataract surgery.^{2,3,4,5,6}

[figure not shown]

Figure 1: Number of LASIK Surgeries per year in the United States

The rising number of such post-LASIK cataract surgery patients has highlighted the limitations of current cataract surgery planning techniques for accurately predicting IOL power in this group. Specifically, refractive results in this group are inferior to those in non-LASIK eyes because of (1) inaccuracy in determining the total corneal refractive power (due to assumptions embedded in diagnostic devices for the anterior-posterior corneal power ratio and corneal refractive index) and (2) incorrect estimation of the effective lens position by many IOL calculation formulas that rely on keratometry readings that are inaccurate for the post-laser cornea. As a result of these limitations, numerous diagnostic and planning methodologies have been proposed and tested to try to improve refractive accuracy in post-LASIK patients. However, despite these efforts, the percentage of post-LASIK cataract surgery patients who are within ± 0.5 D of the predicted MRSE is generally below 50%, with

https://www.statista.com/statistics/271478/number-of-lasik-surgeries-in-the-us/

https://www.lasik.com/articles/lasik-increasing-among-younger-adults/

³ https://www.reviewofoptometry.com/article/when-cataract-develops-long-after-lasik

⁴ https://crstoday.com/articles/2014-jul/choosing-an-iol-after-lasik/

⁵ https://www.reviewofophthalmology.com/article/cataract-patients-younger-every-year

⁶ http://www.nj.com/healthfit/index.ssf/2014/09/advances in cataract surgery allow patients to see their way to a clearer future.html

Vrijman V, Willem van der Linden J, et al. Multifocal intraocular lens implantation after previous corneal refractive laser surgery for myopia. J Cataract Refract Surg Volume 43, Issue 7, July 2017, 909-914.

approximately 80% of these patients within \pm 1.0 D.⁸ In addition, these patients can also have unanticipated post-operative astigmatism, since the original LASIK may have included lenticular astigmatism correction, with removal of the lens unmasking laser-induced corneal astigmatism.⁹

These more variable results contrast with non-LASIK patients undergoing cataract surgery with traditional monofocal IOLs, where the percentage within \pm 0.5 D of the predicted refraction can reach 80% or more depending on surgeon techniques and the patient population. In the Phase III study conducted under IDE G100240 in patients with low preoperative keratometric cylinder, 84% of control eyes implanted with a monofocal IOL were within \pm 0.5 D of the predicted MRSE. While the LAL group performed even better, with 91% within \pm 0.5 D, the main clinical benefit of this improvement in MRSE was a reduction in the number of outliers with significantly higher residual refractive errors. Because the number of such outliers is potentially much higher in post-LASIK eyes undergoing cataract surgery, these patients would likely see a larger clinical benefit by reducing the range of residual MRSE errors due to the inherent difficulties in predicting IOL power in this group. In addition, by producing the desired change in spherocylindrical power of the implanted Light Adjustable Lens (LAL), unanticipated post-operative astigmatism can also be addressed, potentially reducing the need for secondary surgical procedures for the vast majority of post-LASIK patients with residual refractive error.

To evaluate this potential, we propose to compare 6 months postoperative refractive and visual acuity data for LAL eyes compared to a control group of fellow eyes implanted with a commercially available monofocal IOL. Based on the anticipated range of post-operative residual MRSE being within the LAL adjustment range, similar final outcomes are anticipated when compared with the LAL group studied under IDE G100240.

2.1 CLINICAL STUDIES PERFORMED WITH PRIOR VERSION OF THE LIGHT ADJUSTABLE LENS AND LIGHT DELIVERY DEVICE

Phase III Study Conducted Under IDE G100240

A 600 eye prospective, randomized, controlled, multi-center clinical trial of the LAL and LDD designed to evaluate safety and effectiveness over a 12-month period was conducted at 17 sites. In addition to the visual correction of aphakia, reduction in residual spherocylindrical refractive error and improvement in uncorrected visual acuity were evaluated following LAL implantation and subsequent refractive adjustment of the LAL by the LDD.

Eyes with \geq 0.75 and \leq 2.5 diopters (D) of keratometric cylinder were randomly assigned to receive either the LAL or a commercially available, posterior chamber, non-accommodating, control monofocal IOL. Six hundred eyes were implanted with 403 eyes randomized to the LAL group and 197 eyes to the Control group.

⁸ Hamill E, Wang L, Chopra H, Hill W, Koch D. Intraocular lens power calculations in eyes with previous hyperopic laser in situ keratomileusis or photorefractive keratectomy. J Cataract Refract Surg 2017; 43:189-194.

⁹ https://www.reviewofophthalmology.com/article/post-refractive-cataract-choosing-lens-and-target

Co-primary effectiveness endpoints included percent reduction in manifest cylinder, percent mean absolute reduction in manifest refraction spherical equivalent (MRSE), and rotation of the LAL. All primary effectiveness endpoints compared pre-adjustment (LAL) or 17-21 days (Control) to 6 months postoperatively and the first two endpoints compared results between the LAL and Control groups. All three co-primary effectiveness endpoints were met with a p-value <0.0001. The difference in means for percent reduction in manifest cylinder was 54.7%, with a p-value <0.0001. The difference in means for percent reduction in absolute MRSE was 41.1% with a p-value <0.0001. Rotation of the LAL of ≤5 degrees was observed in 96.1% of LAL implanted eyes with both the upper and lower bound of the 95% confidence interval exceeding the requirement of 90%.

100% of eyes in both the LAL and Control groups had BSCVA of 20/40 or better, exceeding the historic grid rate of 92.5% (ISO 11979-7). The incidence of sight-threatening complications and adverse events for the LAL and Control groups were also below the threshold rates calculated from the 1-year historical grid for intraocular lenses (ISO 11979-7, Ophthalmic implants- Intraocular lenses- Part 7: Clinical investigations) except for the category of Secondary Surgical Interventions (SSI), which was significantly higher than the historical rate (p<.05).

On November 22, 2017, the Center for Devices and Radiological Health (CDRH) of the Food and Drug Administration (FDA) approved RxSight's premarket approval application (PMA) for the Light Adjustable Lens (LAL) and Light Delivery Device (LDD) system. This system is indicated for the reduction of residual astigmatism to improve uncorrected visual acuity after removal of the cataractous natural lens by phacoemulsification and implantation of the intraocular lens in the capsular bag; in adult patients:

- With pre-existing corneal astigmatism of ≥ 0.75 diopters
- Without pre-existing macular disease

The system also reduces the likelihood of clinically significant residual spherical refractive errors.

3 STUDY OBJECTIVE

The primary objective of this study is to evaluate, for the visual correction of aphakia, the safety and effectiveness of the RxSight Light Adjustable Lens (LAL) and Light Delivery Device (LDD) to reduce postoperative refractive error and improve uncorrected distance visual acuity in eyes with prior corneal refractive surgery. A control group consisting of fellow eyes implanted with a commercially available monofocal IOL will be used to compare the safety and effectiveness of the LAL.

4 STUDY DESIGN

A prospective, randomized, controlled, multi-center, clinical study will be conducted at a maximum of 8 sites located in the United States. Subjects will be followed for a 6-month period. A minimum of 12 subjects will undergo study implantation at each participating site, with less than 25% of the total study population implanted at one clinical site.

Patients who require bilateral cataract extraction and intraocular lens implantation will be screened for eligibility. If it is determined that the patient may be eligible to participate, study staff will explain the study purpose, procedures, risks/benefits and subject responsibilities to the potential participant. Written informed consent will be obtained prior to any study specific testing. The patient is enrolled upon signing the informed consent. Both eyes of all subjects will be screened for eligibility at the same preoperative visit. A pre-determined randomization scheme will be utilized to designate each of the patient's eyes as the primary eye (LAL) or the fellow eye (Control). The subject's fellow eye will be scheduled for surgery a minimum of 7 days after the primary eye. If surgical complications occur with the primary eye and no LAL is implanted, the subject is exited from the study.

Commencing at the Postop Week 3 visit, all primary eyes will be refracted, undergo visual testing, and receive a power adjustment based on the manifest refraction as determined from testing at 4 meters.

Subjects will return 3 to 7 days after their adjustment and the same measurements performed again. Depending on the adjustment(s) performed, primary eyes will receive one to three adjustments and one to two lock-in treatments. All light treatments are separated by 3 to 7 days.

Postoperatively, all subjects will undergo complete ophthalmic examinations starting with the Postop Week 1 visit. Bilateral ophthalmic examinations can occur if the postoperative visit windows allow. Examinations will occur at regular intervals over a 6-month period to evaluate the safety and effectiveness of the LAL compared to the control. Masked examiners will be utilized at Postop Week 3, Postop Month 3, and Postop Month 6.

For subject complaints related to refractive anisometropia of greater than 1.5 diopters secondary to a refractive surprise with the fellow eye (Control), a secondary surgical intervention (SSI) may be performed on the fellow eye if both the investigator and subject agree it is in the best interest of the subject.

Effectiveness data will be compared between the LAL and Control groups. Safety for all study eyes will be evaluated per ISO 11979-7.

5 OUTCOME PARAMETERS

5.1 EFFECTIVENESS PARAMETER

Primary Endpoints

- Magnitude of manifest cylinder (MRCYL) at Postop Month 6
- Absolute Manifest Refraction Spherical Equivalent (MRSE) at Postop Month 6
- Outcome of best corrected distance visual acuity (BCDVA) of 20/40 or better at Postop Month 6

The MRCYL and MRSE outcomes will be compared between the two study groups, LAL and Control.

Per ISO 11979-7:2014 (E), one-sided upper 95% confidence limit of the percentage of LAL implanted eyes with BCDVA of 20/40 or better at Postop Month 6 is higher than the performance rate of 92.5%. It should be noted that all three effectiveness endpoints must be statistically significant in order to conclude the effectiveness of the LAL. Therefore, no additional significance level adjustment will be performed for these three primary endpoints.

Secondary Endpoints

- Uncorrected distance visual acuity (UCDVA) at Postop Month 6
- UCDVA at Postop Month 6 for subjects measured with keratometric cylinder (Kcyl) <0.75 D in both eyes at the preoperative examination.

The UCDVA outcomes will be compared between the two study groups, LAL and Control.

The secondary effectiveness endpoints will not be tested unless all three primary effectiveness endpoints are statistically significant. Due to this step-down approach, no additional adjustment will be made for the significance levels.

5.2 SAFETY PARAMETERS

• Incidence of ocular serious adverse events including persistent and cumulative events defined per ISO 11979-7.

The incidence of all other adverse events will also be presented.

6 STUDY POPULATION

The study population will consist of up to 120 subjects with implantation of the LAL attempted in the primary eye. Eyes successfully implanted with the LAL will have a commercially available monofocal control IOL, the Sensar AR40e (Abbott Medical Optics), implanted in the fellow eye following cataract removal. All study eyes must have undergone prior corneal refractive surgery, have preoperative keratometric astigmatism of \leq 2.00 D, and meet all the applicable inclusion criteria and none of the exclusion criteria.

Both eyes of all subjects will be screened for eligibility at the same preoperative visit. If at any time during the screening, either eye does not meet inclusion or exclusion criteria, screening for that subject should be discontinued.

6.1 INCLUSION CRITERIA

- Must sign a written Informed Consent form and be willing to undergo cataract surgery for the bilateral implantation of an intraocular lens (IOL).
- Between the ages of 40 and 80 inclusive on the day the cataract surgery is performed.
- Preoperative keratometric cylinder ≤ 2.00 in both eyes.
- History of Laser-Assisted In Situ Keratomileusis (LASIK), Photorefractive Keratectomy (PRK), Laser-Assisted Subepithelial Keratomileusis (LASEK), Epi-LASIK, or Epi-LASEK more than 1 year prior in both eyes.
- Cataract causing reduction in best corrected distance visual acuity (BCDVA) to a level of 20/40 or worse with or without a glare source in both eyes.
- Best corrected distance visual acuity projected (by clinical estimate based upon past ocular history and retinal exam) to be 20/20 or better after cataract removal and IOL implantation in both eyes.
- Clear intraocular media other than cataract in both eyes.
- Willing and able to comply with the requirements for study specific procedures and visits.
- Average dilated pupil diameter of ≥ 7.0 mm in both eyes.
- Able to complete a written questionnaire in English.
- Requires an IOL power within the range available for both the LAL and the Sensar AR40e.

6.2 EXCLUSION CRITERIA

- Prior history of Intacs, RK, CK, AK, Phakic IOL (ICL), Refractive Lens Exchange (RLE), or Corneal Inlay in either eye.
- Clinically significant dry eye syndrome (DES) in either eye.
- Clinically significant corneal haze in either eye.
- Pseudoexfoliation in either eye.
- Pre-existing macular disease in either eye.

- Patients with sufficiently dense cataracts that preclude examination of the macula in either eye.
- Diabetes with any evidence of retinopathy in either eye.
- Evidence of glaucomatous optic neuropathy in either eye.
- History of uveitis in either eye.
- Significant anterior segment pathology, such as rubeosis iridis, aniridia, or iris coloboma in either eye.
- Corneal pathology or corneal dystrophy that is either progressive or sufficient to reduce BCDVA to worse than 20/20 in either eye.
- Evidence of ectasia in either eye.
- Previous intraocular surgery in either eye. Eyes with previous pterygium excision are permitted as long as the pterygium did not extend more than 2mm onto the cornea from the limbus.
- Subjects with serious co-morbid conditions that in the judgment of the investigator makes inclusion in the study not in the best interest of the subject.
- Subjects taking systemic medication that may increase sensitivity to UV light such as tetracycline, doxycycline, psoralens, amiodarone, phenothiazines, chloroquine, hydrochlorothiazide, hypericin, ketoprofen, piroxicam, lomefloxacin, and methoxsalen. LDD treatment in patients taking such medications may lead to irreversible phototoxic damage to the eye. This is only a partial list of photosensitizing medications. Please evaluate all medications that the patient is taking for this effect prior to consideration for implantation.
- Subjects taking a systemic medication that is considered toxic to the retina such as tamoxifen.
- Subjects who the doctor believes will be unable to maintain steady fixation that is necessary for centration of the LDD light treatment in either eye.
- Irregular astigmatism in either eye.
- History of ocular herpes simplex virus in either eye.
- Eye that has been compromised due to previous trauma or developmental defects in which appropriate support of the intraocular lens (IOL) is not possible.
- Current vitreoretinal disease or a high risk for future vitreoretinal disease that may require silicone oil as part of therapy in either eye.

7 STUDY MATERIALS AND METHODS

7.1 DEVICE DESCRIPTION

RxSight's Light Adjustable Lens (LAL) is a silicone intraocular lens whose shape and focusing characteristics can be modified after implantation using an office-based UV light source, the RxSight Light Delivery Device (LDD), to improve uncorrected distance visual acuity.

7.1.1 RXSight Light Adjustable Intraocular Lens

The RxSight Light Adjustable Lens (LAL) is a foldable posterior chamber, UV filtering, three-piece photoreactive silicone lens with blue PMMA (polymethylmethacrylate) modified-C haptics, a 6.0 mm biconvex optic with squared posterior edge, and an overall diameter of 13.0 mm. The LAL optic design (Figure 2) also features a UV filtering posterior surface layer, to further enhance the UV absorbing properties of the LAL lens and limit retinal exposure.

[figure not shown]

FIGURE 2: RXSIGHT LIGHT ADJUSTABLE LENS (LAL)
(A) TOP VIEW AND (B) CROSS-SECTION VIEW OF THE OPTIC SHOWING
LAL WITH A POSTERIOR LAYER

A summary of the LAL design characteristics is presented below:

Lens Optic

- Material: Photo-reactive, UV absorbing Silicone
- Light transmission: UV cut-off at $10\% \text{ T} \ge 392 \text{ nm}$ for all lens power
- Index of refraction: 1.43
- Diopter power: +10 to +15.0 diopters and +25.0 to +30.0 D in 1.0 diopter increments; +16.0 to +24.0 diopters in 0.5 diopter increments
- Optic type: Biconvex
- Optic edge: Square on posterior surface and round on anterior surface
- Overall diameter: 13.0 mm
- Optic diameter: 6.0 mm

Haptics

o Configuration: Modified C

o Material: Blue polymethylmethacrylate

o Haptic angle: 10°

The LAL silicone material is designed to respond to a narrowband UV light by incorporating photoreactive components in the cross-linked silicone lens matrix. Post implantation, the LAL shape may be altered non-invasively (refractive power may be increased or decreased) by photoinitiation of a select spatial intensity profile. The silicone material contains photoreactive additive, which is selectively photo-polymerized in targeted areas upon exposure to the near UV light to alter the lens shape thus modifying spherical and spherocylindrical power of the LAL. The change in the shape becomes permanent when the remaining photoreactive additive is consumed following application of a non-profiled beam of the same ultraviolet light.

7.1.2 LIGHT DELIVERY DEVICE (LDD)

RxSight's Light Delivery Device (LDD) is a UV light projection system (Figure 3) used to induce a predictable change in LAL power after implantation. RxSight's LDD consists of an anterior segment biomicroscope with the addition of an optical projection system, electronic control circuitry, and a UV source. The LDD delivers light profiles with adequate intensity and duration to induce polymerization of photoreactive additive leading to a refractive power change of the LAL. Because this procedure is performed after implantation, residual refractive errors can be minimized, reducing the need for spectacles, corneal refractive procedures, or additional IOL procedures to optimize a patient's vision.

FIGURE 3: RXSIGHT LIGHT DELIVERY DEVICE (LDD)

7.1.3 INSERTION DEVICES

- The RxSight Insertion Device, which is comprised of a re-usable titanium injector and a single-use, non-preloaded polypropylene cartridge with lubricating coating, will be used as the primary device to insert the LAL into the eye.
- The Nichamin III Foldable Lens Inserter (Rhein Medical 05-2349) with the Nichamin II Foldable Lens Insertion Forceps (Rhein Medical 05-2348) can be used as back-up if needed.

7.1.4 INDICATIONS FOR USE

The Light Adjustable Lens and Light Delivery Device system is indicated for the reduction of residual astigmatism to improve uncorrected visual acuity after removal of the cataractous natural lens by phacoemulsification and implantation of the intraocular lens in the capsular bag, in adult patients:

- With pre-existing corneal astigmatism of ≥ 0.75 diopters
- Without pre-existing macular disease.

The system also reduces the likelihood of clinically significant residual spherical refractive errors.

7.2 SUBJECT ENTRY

Patients who require bilateral cataract extraction and intraocular lens implantation will be screened for eligibility. If it is determined that the patient may be eligible to participate, study staff will explain the study purpose, procedures, risk/benefits and subject responsibilities to the potential participant. Written informed consent will be obtained prior to any study specific testing. The patient is enrolled upon signing the informed consent. The subject will sign and date the informed consent form in the presence of the person conducting the consent process. The investigator and/or the person conducting the consent process will also sign and date the consent form. Both eyes of all subjects will be screened for eligibility at the same preoperative visit. A pre-determined randomization scheme will be utilized to designate each of the patient's eyes as the primary eye (LAL) or the fellow eye (Control). The preoperative examination will be performed no more than 60 days prior to surgery for either the primary eye (LAL) or the fellow eye (Control). If the 60-day time period elapses for either eve, it is acceptable for patients to be re-screened by undergoing a complete preoperative examination. The subject's fellow eye will be scheduled for surgery a minimum of 7 days after the primary eye. If surgical complications occur with the primary eye and no LAL is implanted, the subject is exited from the study.

Only subjects meeting all inclusion/exclusion criteria will be implanted. Those subjects who do not meet the inclusion/exclusion requirements will be considered screen failures. Subjects will continue to be enrolled until up to 120 subjects have had LAL implantation attempted in the primary eye. Unique identification numbers will be assigned to each subject.

The implant lens power for the LAL and the Control IOL will be calculated based upon the ocular biometry data and the ASCRS calculator (http://iolcalc.ascrs.org). The investigator should select the IOL formula to be used in a particular subject. The same formula must be used on both eyes of a subject and must be determined prior to randomization. A postoperative spherical equivalent (SE) outcome closest to emmetropia will be targeted in both eyes. The lens power in either eye will not be altered based on intraoperative diagnostics.

7.3 LAL IMPLANTATION AND REFRACTIVE ADJUSTMENT

Each investigative site will follow a standard regimen of pre-, intra-, and postoperative medications to be used in the study that has been reviewed and approved by the study medical monitor. This standard regimen will also specify the ophthalmic viscoelastic device to be used during surgery.

7.3.1 SURGICAL PROCEDURE

The LAL will be implanted using standard microsurgical techniques.

No additional refractive procedures such as limbal relaxing incisions or PRK are allowed on the primary eye (LAL) until after the Postop Month 6 visit.

The surgical procedure will be performed as follows:

- 1. Prepare and drape the eye for surgery in accordance with standard surgical procedures.
- 2. A temporal clear corneal incision will be made using the surgeon's standard instrumentation and techniques.
- 3. Use viscoelastic as agreed upon within the standard regimen to fill the anterior chamber through the incision opening.
- 4. Perform an anterior circular capsulorhexis using standard technique. The capsulorhexis should be well-centered with a 360° overlapping capsular edge to minimize IOL tilt and decentration and longitudinal IOL shift. The capsulorhexis and/or nuclear fragmentation can be performed with a femtosecond laser. Precision pulse capsulotomy (PPC) can also be used to perform the capsulorhexis.
- 5. The surgeon will extract the cataract by phacoemulsification.
- 6. In the event of an intraoperative complication prior to implantation of the LAL, including posterior capsule rupture, zonular rupture, radial capsulorhexis tear, vitreous loss, iris trauma, corneal complications or any intraoperative abnormality that may affect the postoperative pupillary dilation, or the centration or tilt of the intraocular lens, do not implant the LAL.

[figure not shown]
- 8. Verify proper orientation of the LAL
- 9. Aspirate any residual viscoelastic from the eye using a preferred technique.
- 10. The wound may close without suturing. If the unsutured wound is not watertight, close it with a either a suture using standard technique or an ocular sealant (ReSure Sealant).
- 11. After completion of the surgery, postoperative medications should be administered per the agreed upon investigative site standard regimen.

12. The subject will be provided with two pairs of RxSight approved UV protective spectacles (one clear and one tinted) to protect the implanted LAL from extraneous sources of UV light. It is important to direct the subject to follow all instructions that are provided with the UV protective spectacles.

If a patch was used at the conclusion of surgery, the subject will wait for the surgeon to remove the patch. Once removed, the subject will begin wear of the UV protective eyewear as instructed.

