7.4 CONTROL LENS IMPLANTATION

will be implanted in the subject's fellow eye a minimum of 7 days after the LAL has been successfully implanted in the primary eye. Standard microsurgical techniques will be employed. A clear corneal incision of temporal orientation will be made. Limbal relaxing incisions (LRI) are not to be used during surgery to implant the Control lens.

For subject complaints related to refractive anisometropia of greater than 1.5 diopters secondary to a refractive surprise with the fellow eye (Control), a secondary surgical intervention (SSI) may be performed on the fellow eye if both the investigator and subject agree it is in the best interest of the subject.

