7.8.3 SUBJECT WITHDRAWAL DUE TO INTRAOPERATIVE COMPLICATIONS PRIOR TO IMPLANTATION

Subjects that meet all inclusion/exclusion criteria but do not undergo implantation of the LAL due to intraoperative complications prior to introduction of the LAL will be followed to resolution of any adverse events and then exited from the study.

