8.4.3 FULL ANALYSIS SET (FAS)

The Full Analysis Set (FAS) is a subset of the ITT which consists of the ITT subjects that have the LAL implanted in one eye and the Control lens in the other eye. The primary analyses for the primary and secondary effectiveness endpoints will be based on the FAS. For the FAS subjects that do not have the Postop Month 6 data, the missing MRCYL, MRSE, and UCDVA will be assumed to the same for their two eyes in the primary analyses. Different imputations will be included in the sensitivity analyses described in Section 8.5.2 below and in the SAP of this study protocol.

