 ECD at Preop × 100% Δ %ECL = %ECL of LAL eye - %ECL for Control eye

The descriptive statistics for continuous variables will be used to summarize Δ %ECL. A one-sided 95% upper confidence limit for mean Δ %ECL will be derived based on t-distribution. If the Nichamin III foldable lens inserter is used during the study, the analyses may be stratified by the subjects with versus without the use of Nichamin III foldable lens inserter.

It should be noted that, per the previous PMA clinical study, the standard deviation of $\Delta\%$ ECL is estimated as 4%. For a statistical hypotheses test of H0: Mean of $\Delta\%$ ECL $\geq 5\%$ versus Ha: Mean of $\Delta\%$ ECL < 5% (i.e. the mean of %ECL in the LAL eyes is at most 5% higher than that in the control eyes) with a one-sided significance level of 0.05, a sample size of 100 bilateral subjects at 6 months can provide the following statistical power at different true values of Mean of $\Delta\%$ ECL. The derived one-sided 95% upper confidence limit of mean $\Delta\%$ ECL described above can be used to compare against the 5% used in the statistical hypotheses described above.

True µ∆%ecl	Statistical Power
0.0%	>0.99
0.5%	>0.99
1.0%	>0.99
1.5%	>0.99
2.0%	>0.99

2.5%	>0.99
3.0%	>0.99
3.5%	0.98
4.0%	0.80

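### Pairs are selected on complication-free surgery in the LAL eye but not in the Control eye, which can tilt the paired comparisons, the supportive ECD comparison most of all, towards the LAL

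*Combined protocol and SAP*

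**What the plan says.** **LAL eye.** Section 7.3.1, step 6, opens "In the event of an intraoperative complication prior to implantation of the LAL, including posterior capsule rupture, zonular rupture, radial capsulorhexis tear, vitreous loss". It goes on to iris trauma and "corneal complications or any intraoperative abnormality". The step closes by describing the abnormalities meant and giving the instruction: "that may affect the postoperative pupillary dilation, or the centration or tilt of the intraocular lens, do not implant the LAL". Section 7.2 adds: "If surgical complications occur with the primary eye and no LAL is implanted, the subject is exited from the study". Under 7.8.3 such subjects "will be followed to resolution of any adverse events and then exited from the study". Section 8.4.2 removes them from the statistical analyses, and the safety population in 8.4.1 begins only when the LAL touches the eye.

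**Control eye.** Surgery follows at least 7 days later. On technique, section 7.4 says "Standard microsurgical techniques will be employed". It also gives the incision, a ban on limbal relaxing incisions and the provision for secondary surgery for anisometropia. Its readable text has no rule for an intraoperative complication.

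**Analysis sets.** The FAS "consists of the ITT subjects that have the LAL implanted in one eye and the Control lens in the other eye". The per-protocol set (8.4.4) removes major protocol deviations, and a surgical complication is not listed as one.

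**ECD.** Section 8.6 defines the within-subject difference in percent endothelial cell loss (Δ%ECL, LAL minus Control). A one-sided 95% upper limit for its mean "will be derived based on t-distribution" and can be set against 5%. Section 8.7.1 attributes cell loss mainly to surgical trauma to the cornea and plans the same analyses on Week 3 data.

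**The concern.** Randomising the two eyes of a subject makes the pair comparable before surgery. Step 6 then acts after randomisation on one eye only: a pair survives if the LAL eye had no listed complication before lens placement, whatever later happens in the Control eye. If some complicated Control eyes are implanted and do worse, all three refractive and acuity differences and Δ%ECL move in the LAL's favour.

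ECD is the most exposed outcome on the protocol's own reasoning, since surgical trauma is named as the main cause of cell loss and corneal complications are among the step-6 triggers. Extra loss in Control eyes lowers mean Δ%ECL and makes it easier for the upper limit to fall below 5%.

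No planned analysis would show this. Section 8.5.2 varies the imputation and uses the per-protocol set and, for BCDVA, the Best-Case cohort. Section 8.5.3 covers demographics and site. The only stratification offered for Δ%ECL is by lens inserter.

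**Working it through.** **Inputs from the plan (8.6):** SD of Δ%ECL 4%, 100 pairs, margin 5%, one-sided level 0.05. Planned refractive differences (8.1): −0.375 D for MRCYL and −0.25 D for |MRSE|.

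**Step 1: reproduce the plan's ECD power.** The standard error is 4/√100 = 0.40 points. The paired t-test has noncentrality (5 − μ)/0.40 on 99 degrees of freedom.
- μ = 4.0%: noncentrality 2.5, power 0.799 (plan 0.80)
- μ = 3.5%: noncentrality 3.75, power 0.981 (plan 0.98)
- μ = 3.0%: noncentrality 5.0, power 0.9996 (plan >0.99)

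The table reproduces.

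**Step 2: model the tilt.** Let r be the share of Control eyes kept after a step-6 complication and x the extra cell loss in those eyes, in percentage points. The documents give neither, so both are assumptions. LAL eyes have no such complications by selection. Then:
- shift in mean Δ%ECL = −r × x
- SD of the difference = √(4² + r(1 − r)x²)

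Example: r = 2% and x = 20 give a shift of −0.40, which is one planning standard error, and an SD of √(16 + 0.02 × 0.98 × 400) = √23.84 = 4.88.

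**Step 3: chance of falsely clearing 5%.** Simulation of 40,000 trials with 100 pairs each. Differences are normal with mean 5 and SD 4, less x with probability r. The result is the share of trials in which the t-based one-sided 95% upper limit lies below 5.

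| r | x = 10: shift | chance | x = 20: shift | chance |
|---|---|---|---|---|
| 0 | 0 | 0.05 | 0 | 0.05 |
| 1% | −0.10 | 0.08 | −0.20 | 0.10 |
| 2% | −0.20 | 0.12 | −0.40 | 0.18 |
| 4% | −0.40 | 0.22 | −0.80 | 0.39 |

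These apply only at a true mean of exactly 5% in uncomplicated pairs. At 3% or below, the untilted test already clears the margin with probability above 0.99 (step 1), and rightly, so the tilt changes nothing.

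**Step 4: refraction.** With an assumed excess of 1.0 D in affected Control eyes, the shift is r × 1.0 D. For r = 1–4% this is 0.01–0.04 D. Against |MRSE| it is 0.01/0.25 = 4% to 0.04/0.25 = 16% of the planned difference. Against MRCYL it is 0.01/0.375 = 3% to 0.04/0.375 = 11%.

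**Step 5: same filter on both eyes.** If pairs whose Control eye had a step-6 complication are removed, r = 0 in the analysed pairs. Under this model the shift vanishes and the 0.05 level and the plan's power return.

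**The case against.** Several points on the other side stand and limit the concern.

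- **Silence.** Nothing says that a complicated Control eye is to be implanted or kept. Section 7.4 also starts mid-sentence where text was removed. The strongest supportable wording is that such an eye may be implanted.
- **Partial offset.** Section 8.3 foresees failed Control implantation, and Control eyes left without the lens drop out of the FAS. A reader might infer that complication-free LAL surgery is being compared with unselected Control surgery. The documents do not support that: both eyes pass the same screening, and only complicated Control eyes that still receive the lens matter. Nor is every LAL eye free of complications, because those arising after placement stay in.
- **Existing data.** Table 3 already schedules adverse events at the Operative Control visit, and 8.6 summarises ocular events at the operative visit. Many step-6 events would probably be captured. What is missing is a flag tied to the step-6 list and a planned use of it.
- **Assumed size.** An extra loss of 10–20 points is 2.5 to 5 planning SDs, and most step-6 triggers are not corneal. It is tempting to read the increase from 110 implanted to 120 attempted in 8.1 as a complication rate of 10/120 = 8.3%. That is a planning allowance for failed LAL implantation, not a rate of retained Control complications, and it is not used here.
- **Status of ECD.** It is neither a primary nor a secondary endpoint. The limit is supportive, and the Week 3 look is administrative and cannot stop the study.

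None of this removes the one-sided selection or supplies an analysis that would reveal its effect.

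**Conclusion.** The concern holds as a possible tilt in one direction that the plan leaves unexamined. Entry to the paired analyses depends on complication-free surgery up to lens placement in the LAL eye, with no matching condition on the Control eye. ECD is most exposed: under the stated assumptions the chance of wrongly clearing 5% is 0.08–0.39 instead of 0.05, but only if the true mean lies at the margin. The refractive shift is probably small, about 0.01–0.04 D in |MRSE| under an assumed 1.0 D excess.

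A reader might infer that the ECD conclusion or the primary refractive results are unreliable. The documents do not support that. They give neither the share of retained complicated Control eyes nor the excess loss, and the ECD conclusion would stand at a true mean of 3% or below. Nor do they support replacing the planned comparison by the filtered one. Step 6 includes an open-ended judgement about abnormalities. In the LAL eye that judgement ends participation, whereas in the Control eye it would carry no consequence, so it may be applied differently.

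**What to change.** 1. At the Operative Control visit, where adverse events are already recorded, flag any event on the step-6 list that occurs before lens placement.
2. In 8.5.2 and 8.6, prespecify a sensitivity analysis that leaves out pairs whose Control eye carries this flag. Repeat on the remaining pairs the paired tests of MRCYL, |MRSE| and UCDVA and the one-sided 95% limit for mean Δ%ECL, the latter at the Week 3 interim and at Month 6. Report it beside the planned analysis, which stays the main one.
3. Report the number of subjects exited because of complications in the LAL eye.

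The cost is one case report form item and a repeat of analyses already planned. A few pairs are lost in the sensitivity set, and its ECD result may be less favourable. No change to surgical management is proposed.
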